5.1 Analysis Sets

The following analysis sets will be used for the data analysis:

Extension Full Analysis Set (extension FAS): The extension FAS will be comprised of all subjects enrolled in the extension study.

(In this document extension FAS is referred to as FAS).

Of note, FAS will comprise only the subjects from extension whereas safety set will include from core or extension, safety set will be larger than FAS.

Up-titration Subset: The up-titration subset will be comprised of all subjects from the extension FAS set who received at least one dose of the up-titration dose.

[REDACTED]

Safety set: The safety set includes all subjects enrolled in the core study who took at least 1 dose of study treatment during the core study. Subjects will be evaluated according to treatment received.

5.2 Treatment groups

Unless otherwise specified, the summaries will be performed by the treatment sequence.

- Efficacy:

- AIN457 10 mg/kg - 75 mg -150 mg
- AIN457 10 mg/kg - 150 mg
- Placebo - AIN457 75 mg – 150 mg
- Placebo - AIN457 150 mg
- Any AIN457 75 mg
- Any AIN457 150 mg

After week 52 the combination of assigned treatments will also be shown as follows:

- AIN457 75 mg & Placebo - AIN457 75 mg
- AIN457 150 mg & Placebo - AIN457 150 mg

Tables on MMRM or MI estimates will be summarized only for the AIN457 10 mg/kg - 150 mg originally randomized group.

- Safety
 - Any AIN457 75 mg
 - Any AIN457 150 mg
 - Any AIN457

Placebo treatment group will be displayed only in safety listings and in in-tex safety tables.

6 Subgroup definitions

The primary endpoint(s) and secondary endpoints will be evaluated by TNF-alpha inhibitor status.

7 Assessment windows, baseline and post baseline definitions, missing data handling

Baseline and post-baseline definitions

In general [REDACTED], a *baseline* value refers to the last measurement made prior to administration of the first dose of study treatment. A post-baseline value refers to a measurement taken after the first dose of study treatment.

For X-ray, a baseline value is the last measurement prior to dosing if available, or the first value within 30 days post dosing if no other value is available prior to dosing.

[REDACTED]

For post baseline visit -windows during the core study the following applies (unless otherwise specified):

For quantitative variables, the closest to the actual visit is chosen (if two assessment have the same distance, then the earlier now will be chosen)/

For qualitative variables, the worst record is selected. It is noted that in the analysis performed, worst case is always well defined (e.g., for urine protein values “+” and “++” the worse case is defined as “++”).

Analysis visit windows

Analysis visit windows will be used for the data that is summarized by visit; they are based on the study evaluation schedule and comprise a set of days around the nominal visit day. For any assessment, there are protocol defined scheduled visits around which analysis visit windows were created to cover the complete range of days within the study. The analysis visit windows and rules for dealing with multiple measurements within the windows are described in [Section 19.1](#).

For visits that occur after week 104, the recorded nominal visit data will be considered.

8 Subject disposition, background and demographic characteristics

8.1 Subject disposition

The number of subjects enrolled in the extension was presented at the will be presented. The number and percentage of subjects in the FAS who completed the study and who discontinued the study prematurely (including the reason for discontinuation) will be presented for each treatment group and all subjects.

For the week 260 final DBL, for each protocol deviation (PD), the number and percentage of subjects for whom the PD applies will be tabulated.

8.2 Background and demographic characteristics

Demographics and Baseline characteristics for FAS as well as for the subjects in FAS that up-titrated will be displayed. The following common background and demographic variables will be analyzed for these subjects:

Continuous variables:

- Age (which is derived from date of birth and the screening assessment date)
- Height
- Weight
- Body mass index (BMI) = (body weight in kilograms) / (height in meters)²

Categorical variables:

- Age categories (<65 years, 65 years and older, 75 years and older)
- Gender
- Race
- Ethnicity
- Weight (<70 kg, 70-90 kg, >90kg)
- Smoking status at baseline

The following disease specific baseline characteristics and history of disease will be summarized as well:

Patient's global assessment of disease activity and other ASAS components, [REDACTED], prior use of TNF-alpha inhibitors, number of prior TNF alpha inhibitors, use (yes/no) and separate dose of methotrexate (mg/week), sulfasalazine (g/day) and systemic corticosteroids (mg/day) at randomization, time since first diagnosis of AS (years), modified New York criteria for AS, HLA-B27, [REDACTED]
[REDACTED]

Summary statistics will be presented for continuous variables for each treatment group and for all subjects (total) in the FAS as well as for the FAS patients who up-titrated during the study. The number and percentage of subjects in each category will be presented for categorical variables for each treatment and all subjects (total) in the FAS.

9 Medical history

Any condition entered on the *Relevant medical history / current medical conditions* CRF is to be coded using the MedDRA dictionary. Summaries by system organ class (SOC) and preferred term (PT) of the MedDRA dictionary were already presented in the SAF population during the core study. The same stands for summaries for cardiovascular medical history and Ankylosing Spondylitis medical history.

Chest x-ray (screening) results will not be listed.

10 Study medication

The analysis of study treatment data will be based on the safety set. The number of active injections will be summarized by treatment group. The duration of exposure to study treatment will also be summarized by treatment group. In addition, the number and percentage of subjects with cumulative exposure levels (e.g. any exposure, ≥ 1 week, ≥ 2 weeks, ≥ 3 weeks, ≥ 4 weeks, ≥ 8 weeks, etc.) will be presented.

Duration of exposure will be calculated as time from first dose of study treatment in core to the minimum of (last dose of the treatment + 84 days) and (last visit date). For subjects who discontinue, this will be the subject's last visit in the corresponding treatment period.

Duration of exposure (years) = duration of exposure (days) / 365.25

Duration of exposure (100 subject years) = duration of exposure (years) / 100

The analyses of duration of exposure described above will be done for the entire study treatment period.

11 Concomitant medication

Concomitant medication in extension

Concomitant medications in extension will be summarized by treatment dose. Any medication given at least once between the start of the first dose in this extension trial and 84 days after the last study visit in the extension study will be a concomitant medication, including those which were started before Week 104E1 and continued into the extension study where study treatment is administered.

Medications will be presented in alphabetical order, by Anatomical Therapeutic Classification (ATC) codes and grouped by anatomical main group. Tables will show the overall number and percentage of subjects receiving at least one treatment of a particular ATC code and at least one treatment in a particular anatomical main group.

Significant concomitant non-drug therapies (e.g. prior surgeries) and procedures will be summarized by primary system organ class and MedDRA preferred term.

Prior surgeries and procedures are defined as surgeries and procedures executed prior to the first study dose. Any surgeries and procedures started between the day of the first dose of study treatment and within 84 days after the last dose will be concomitant surgeries and procedures, including those which were started pre-baseline and continued into the period where study treatment is administered.

The number and percentage of subjects receiving prior and concomitant ankylosing spondylitis therapy will be presented by treatment group as well as the reasons for stopping their therapies (primary lack of efficacy, secondary lack of efficacy, lack of tolerability, other) and the total duration of exposure to psoriatic arthritis therapies previously.

Data will be analyzed on SAF.

Concomitant medication in core or extension

Concomitant medications data collected in core and extension will be combined together. Data for concomitant medications for core are collected in core study and the same will be used.

Any medication given at least once between the start of the first dose in core trial and the date of the last study visit in the extension trial will be summarized. Data will be analyzed on safety set.

Prior or concomitant medication will be identified by comparing recorded or imputed start and end dates of medication taken to the reference start date. Further rules will be given in PDS.

12 Efficacy evaluation

12.1 Description of efficacy variables

Assessment of Spondyloarthritis International Society criteria (ASAS) response criteria

The ASAS response measures consist of the following assessment domains ([Sieper 2009](#)).

[figure not shown]
Main ASAS domains:

1. Patient's global assessment of disease activity measured on a VAS scale
2. Patient's assessment of back pain, represented by either total or nocturnal pain scores, both measured on a VAS scale. *For ASAS response analyses, the total back pain will be used.*
3. Function represented by BASFI average of 10 questions regarding ability to perform specific tasks as measured by VAS scale

4. Inflammation represented by mean duration and severity of morning stiffness, represented by the average of the last 2 questions on the 6-question BASDAI as measured by VAS scale (at least one question is needed)

Additional assessment domains:

5. [REDACTED]
6. [REDACTED]

ASAS components

Patient's global assessment of disease activity (VAS)

The patient's global assessment of disease activity will be performed using a 100 mm visual analog scale (VAS) ranging from not severe to very severe, after the question "*How active was your disease on average during the last week?*".

Patient's assessment of total inflammatory back pain and nocturnal back pain intensity (VAS)

The patient's assessment of inflammatory back pain will be performed using a 100 mm VAS ranging from no pain to unbearable pain, after the question "*Based on your assessment, please*

indicate what is the amount of back pain at any time that you experienced during the last week?” and “Based on your assessment, please indicate what is the amount of back pain at night that you experienced during the last week? ”.

Bath Ankylosing Spondylitis Functional Index (BASFI)

The BASFI is a set of 10 questions designed to determine the degree of functional limitation in those subjects with AS. The ten questions were chosen with a major input from subjects with AS. The first 8 questions consider activities related to functional anatomy. The final 2 questions assess the subjects’ ability to cope with everyday life. A 100 mm VAS is used to answer the questions. The mean of the ten scales gives the BASFI score – a value between 0 and 10.

In the case that some of the BASFI questions are missing then the average of the non-missing items will be utilized ([Braun 2009](#), [van Tubergen 2001](#))

Bath Ankylosing Spondylitis Disease Activity Index (BASDAI)

The gold standard for measuring and evaluating disease activity in AS is the BASDAI. The BASDAI consists of a 0 through 10 scale (0 being no problem and 10 being the worst problem), which is used to answer 6 questions pertaining to the 5 major symptoms of AS:

1. Fatigue
2. Spinal pain
3. Joint pain / swelling
4. Areas of localized tenderness (called enthesitis, or inflammation of tendons and ligaments)
5. Morning stiffness duration
6. Morning stiffness severity

To give each symptom equal weighting, the mean (average) of the two scores relating to morning stiffness is taken. The mean of questions 5 and 6 is added to the score from questions 1-4. If one of questions 5 or 6 is missing, then the non-missing one should be added. The resulting 0 to 50 score is divided by 5 to give a final 0 – 10 BASDAI score. Scores of 4 or greater suggest suboptimal control of disease, and subjects with scores of 4 or greater are usually good candidates for either a change in their medical therapy or for enrollment in clinical trials evaluating new drug therapies directed at AS. BASDAI is a quick and simple index taking between 30 secs and 2 mins to complete.

At least 4 questions should be non-missing to calculate the BASDAI score. Otherwise, BASDAI score will be missing ([Haywood 2002](#)). If both Q5 and Q6 are missing or one of Q1 to Q4 is missing the total sum should be divided by 4 instead of 5. If two of Q1 to Q4 are missing and both Q5 and Q6 are not missing the sum should be divided by 3.

Bath Ankylosing Spondylitis Metrology Index (BASMI linear)

The BASMI is a validated instrument that uses the minimum number of clinically appropriate measurements that assess accurately axial status, with the goal to define clinically significant changes in spinal movement. Parameters include:

1. lateral lumbar flexion (cm)
2. tragus-to-wall distance (cm)

3. lumbar flexion (modified Schober) (cm)
4. maximal intermalleolar distance (cm)
5. cervical rotation angle (°)

Additionally, the following assessments should be taken:

6. occiput-to-wall distance
7. chest expansion

The assessments A of the first five components into the scores S using the equations are given in [Table 12-1 \(van der Heijde et al, 2013\)](#). All 5 components should be non-missing to calculate BASMI.

[figure not shown]
Table 12-1 Equations for the conversion of the assessments A into scores S for the five components of the BASMI linear

[figure not shown]
	$S = 0$ if	Between 0 and 10	$S = 10$ if
Lateral lumbar flexion* (cm)	$A \geq 21.1$	$S = (21.1 - A)/2.1$	$A \leq 0.1$
Tragus-to-wall distance* (cm)	$A \leq 8$	$S = (A - 8)/3$	$A \geq 38$
Lumbar flexion (modified Schober) (cm)	$A \geq 7.4$	$S = (7.4 - A)/0.7$	$A \leq 0.4$
Intermalleolar distance (cm)	$A \geq 124.5$	$S = (124.5 - A)/10$	$A \leq 24.5$
Cervical rotation angle*(°)	$A \geq 89.3$	$S = (89.3 - A)/8.5$	$A \leq 4.3$

[figure not shown]
* For lateral lumbar flexion, tragus-to-wall distance, and cervical rotation the average of right and left should be taken.

[figure not shown]
If a score lies beyond the range 0-10, the values 0 or 10 have to be used, respectively.

[figure not shown]
For facilitating computer calculations with "if ... then ... else" fields in a table calculation program such as Microsoft Excel, the limits of the linear ranges are also given. The $\text{BASMI}_{\text{linear}}$ is the mean of the five scores.

12.3 Handling of missing data

Missing data

Analysis of study data will be based on the observed data. In addition to the observed data approach, multiple imputation technique will be employed for the following binary variables: ASAS20, ASAS40, [REDACTED]

[REDACTED] Analysis will be limited to the higher originally randomized dose (AIN457 10 mg/kg - 150 mg)

For analyses of these parameters, if all post baseline values are missing then these missing values will not be imputed and this subject will be removed from the analysis of the corresponding variable, i.e. it might be that the number of subjects providing data to an analysis is smaller than the number of subjects in the FAS.

[REDACTED] mixed model repeated measures (MMRM) will be fitted assuming random missingness to assess the durability of secukinumab effect. The explanatory variables will be baseline score, weight,

TNF α status, analysis visit, and analysis visit by baseline score. An unstructured correlation matrix will be used thus allowing adjustment for correlations between time points within subjects. This analysis will be done on the entire treatment period for the AIN457 10 mg/kg - 150 mg treatment arm.

13 Analysis of the primary variable(s)

13.1 Variable(s)

The primary efficacy variable is the clinical response to treatment according to the ASAS20 over time up to Week 260. The analysis of the primary variable will be based on the FAS subjects.

13.2 Statistical model, hypothesis, and method of analysis

No formal hypotheses are proposed for this study. The proportion of subjects meeting the ASAS20 will be descriptively summarized for each treatment over time from week 1 in core study onwards and treatments will be compared by providing 95% CIs for the proportion of patients responding to treatment according to the ASAS20 criteria. Results will be presented for the FAS, as well as subgroups by TNF α status (naive or IR).

13.3 Supportive analyses

[figure not shown]
Sensitivity analyses will be performed by using multiple imputation for missing assessments for ASAS20/40 to assess the robustness of missing data handling.

14 Analysis of secondary [REDACTED] variables

14.1 Efficacy variables

Secondary [REDACTED] variables include:

- the proportion of subjects achieving ASAS40

For binary variables, the proportion of responders along with the 95% CI will be presented by groups according to the treatment sequence over analysis visits. For continuous variables, the change from core baseline will be summarized.

Results will be presented for the FAS, as well as subgroups by TNF α status (naive or IR) for the following variables: ASAS40, [REDACTED]

Graphical representation (line plots) regarding the response over time for the following measures will be provided in the observed data: ASAS20/40, [REDACTED]

[REDACTED] will also be graphically illustrated. The above mentioned figures will show the originally randomized AIN457 treatment groups.

Cumulative probability plots will be employed to display the change from baseline to week 208 illustrating the progression of subjects after 4 years [REDACTED]

Additional figures as in line plots, illustrating the up-titration effect of treatment will be created for the following parameters: ASAS20/40, [REDACTED]

ASAS20

The ASAS Response Criteria (ASAS20) is defined as an improvement of $\geq 20\%$ and ≥ 1 unit on a scale of 10 in at least three of the four main domains and no worsening of $\geq 20\%$ and ≥ 1 unit on a scale of 10 in the remaining domain.

The percentage of subjects experiencing ASAS20 response, followed by the respective 95% CI, will be presented by treatment sequence up to week 260 based on the observed data. The respective summaries will also be provided by TNF- α IR status.

Additional analysis will be based on the imputed responses only for the AIN457 150 mg group.

The percentage of subjects (and the 95% CI) experiencing ASAS20 response after up-titration will be presented in separate tables (observed data). Patients who had at least 1 dose of the up-titrated dose will be included.

[figure not shown]
ASAS40

[figure not shown]
The ASAS 40 response is defined as an improvement of $\geq 40\%$ and ≥ 2 units on a scale of 10 in at least three of the four main domains and no worsening at all in the remaining domain.

[figure not shown]
[figure not shown]
The percentage of subjects experiencing ASAS40 response, followed by the respective 95% CI will be presented by treatment sequence up to week 260 based on the observed data. The respective summaries will also be provided by TNF- α IR status.

[figure not shown]
Additional analysis will be based on the imputed responses only for the AIN457 150 mg group.

[figure not shown]
The percentage of subjects (and the 95% CI) experiencing ASAS40 response after up-titration will be presented in separate tables (observed data). Patients who had at least 1 dose of the up-titrated dose will be included.

16 Safety evaluation

Safety analyses will be done on the safety set.

Analysis of adverse events will be based on treatment emergent events, which are defined as events started after the first dose of study treatment in core study or events present prior to the first dose of study treatment in core study but increased in severity based on preferred term and within last dose + 84 days.

Other safety variables will be based on on-treatment events, which are defined as any events that happened after first dose of study treatment and within last dose + 84 days.

Summaries (other than by visit analysis) will be presented cumulatively from core and extension. For subjects who switched from placebo to secukinumab in the core study, their data prior to switch will not be reported. Safety on placebo will be based on the core study and will be reported in the in-text outputs and study listings.

Unless otherwise mentioned, by visit analysis will include the following visits: Baseline visit from core, Week 104E1 visit and all visits in extension. Summaries will be performed for all the events that happened within the last dose + 84 days.

Safety analyses will be performed on treatment received or actual treatment as described below:

The actual treatment or treatment received for summaries of safety data will differ to the treatment assigned at randomization if a subject received the wrong treatment during the entire study or if the subject up-titrated to a higher dose..

Subjects who switch treatment during the study (e.g. from placebo to active treatment, or escalated the dose) will be counted to both groups using the corresponding start and stop exposure date.

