Study/investigational treatment discontinuation	Point/time when subject permanently stops taking study/investigational treatment for any reason; may or may not also be the point/time of premature subject withdrawal
Subject Number	A number assigned to each subject who enrolls into the study
Variable	Information used in the data analysis; derived directly or indirectly from data collected using specified assessments at specified time points

Amendment 1

Amendment rationale

This protocol amendment is issued for the following reasons:

[figure not shown]
1. After approval and implementation of Amendment 1, all patients will receive study medication in an open-label fashion. The study medication for subjects on the 75 mg treatment arm will be re-evaluated for patients whose overall therapeutic response is not fully achieved with the current dose of 75 mg and may improve with a higher dose (150 mg s.c. every 4 weeks), as judged by the investigator at any time after implementation of Protocol Amendment 1.

The 52-week efficacy data from the pivotal Phase 3 trial (CAIN457F2310) of secukinumab in active moderate to severe ankylosing spondylitis (AS) showed that secukinumab 150 mg s.c. provides robust, statistically significant, and clinically meaningful efficacy versus placebo in the treatment of AS when administered at Baseline (BSL), Weeks 1, 2, and 3, and every 4 weeks thereafter starting at Week 4, as reflected in an ASAS 20 response rate of approximately 60% at the Week 16 primary endpoint ([Figure 0-1](#)). A higher dose intravenous (i.v.) loading regimen of 10 mg/kg at BSL, Weeks 2 and 4 administered in CAIN457F2305 did not provide any additional efficacy benefit to the 150 mg s.c. maintenance regimen, with a similar Week 16 ASAS 20 response rate of approximately 60% in the 10 mg/kg - 150 mg arm.

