The treatment will be offered in prefilled syringes (PFS) in the extension study. This is a change from the core study, which used s.c. injections prepared from lyophilisate. Subjects will be instructed in detail how to self-administer the s.c. injection using the PFS formulation. Each injection will be administered into an appropriate injection site of the body (thighs, arms, or abdomen). For the first 3 months of the study (through Week 116), all injections will be performed at the study site. Starting on Week 120, the subject is allowed to self-administer the study medication at home or continue to present at monthly intervals to the study site for injection administrations, based on the subject's preference and the investigator's judgment. Site staff will administer the injection to subjects who are not able or unwilling to self-administer the PFS injection.

At Week 156 or after approval and implementation of Protocol Amendment 1, whichever occurs first, site personnel and the subject will be unblinded as to their current treatment regimen. The subject will continue to receive the same dose of secukinumab and will no longer receive the placebo PFS. After approval and implementation of Protocol Amendment 1, the study medication for subjects on the 75 mg treatment arm should be escalated from 75 mg s.c. to 150 mg s.c. every 4 weeks for patients whose overall therapeutic response is not fully achieved with the current dose of 75 mg and may improve with a higher dose, as judged by the investigator. The escalation of the study medication may be determined at any site visit..

[figure not shown]
For patients escalated to secukinumab 150 mg s.c. every 4 weeks, no dose reduction can be performed and if the patient is unable to tolerate the 150 mg dose of secukinumab alternative treatment options should be considered only after discontinuation from the study ([Section 5.5.9](#)).

Assessments for safety, efficacy, [REDACTED] will be performed according to the assessment schedule ([Table 6-1](#), [Table 6-2](#), [Table 6-3](#)).

A follow-up visit is to be done 12 weeks after the last study treatment administration for all subjects (regardless of whether they complete the entire study as planned or discontinue prematurely).

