5.5.5 Permitted dose adjustments and interruptions of study treatment

Study treatment dose adjustments are not permitted until approval and implementation of Protocol Amendment 1. After approval and implementation of the Protocol Amendment 1, the

study medication for subjects on the 75 mg treatment arm should be escalated from 75 mg s.c. to 150 mg s.c. every 4 weeks for patients whose overall therapeutic response is not fully achieved with the current dose of 75 mg and may improve with a higher dose, as judged by the investigator. The escalation of the study medication may be determined at any site visit. For patients escalated to 150 mg, no dose reduction can be performed at a later time point.

Study treatment interruption is permitted only if, in the opinion of the investigator, a subject is deemed to be placed at a significant safety risk unless dosing is temporarily interrupted. In such cases, study treatment should be interrupted only during the time that this risk is present and ongoing. Study treatment can be restarted at the next scheduled visit after resolution of the safety risk.

The effect of secukinumab on live vaccines is unknown; therefore live vaccines should not be administered during participation in the study. In case a live vaccine has been administered due to a medical urgency, study treatment should be interrupted for 12 weeks.

These changes must be recorded on the Dosage Administration Record CRF.

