Post-baseline safety during the core study phase	Notable abnormalities (e.g. lab)	The most extreme measurement in the window will be used. Note this means a patient can have a notably high and notably low measurement within a window.

No visit windows were used in case of up-titration. The before up-titration measurement is considered as the last visit measurement, performed on or before the date that patient took the up-titration dose. The up-titration data analysis will be based on week intervals; it is accounting for the time period between the actual date of exposure to the up-titrated dose and the last visit date of the subject:

- 4 – 8 weeks after up-titration
- 12 – 20 weeks after up-titration
- 24 – 32 weeks after up-titration
- 36 – 44 weeks after up-titration
- 48 – 60 weeks after up-titration

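### The line plots of the up-titration effect start from a measurement that often is, or informed, the decision to escalate, so part of any apparent gain can be regression to the mean

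*SAP*

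**What the plan says.** **Who is escalated.** Protocol 5.5.5 moves subjects on 75 mg to 150 mg "for patients whose overall therapeutic response is not fully achieved with the current dose of 75 mg", if the investigator also thinks a higher dose may help. On timing it says: "The escalation of the study medication may be determined at any site visit". Once Amendment 1 is implemented, "all patients will receive study medication in an open-label fashion" (Protocol, Amendment 1 rationale), so the judgement is made with the dose known.

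**Who is analysed.** The up-titration subset is "all subjects from the extension FAS set who received at least one dose of the up-titration dose" (SAP 5.1). It contains escalated subjects only.

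**What the before-value is.** SAP 19.1: "The before up-titration measurement is considered as the last visit measurement, performed on or before the date that patient took the up-titration dose". Later values are grouped by weeks since up-titration, from 4–8 up to 48–60 weeks.

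**How the outputs are described.** SAP 14.1 describes the tables neutrally, as ASAS20 and ASAS40 response after up-titration on observed data. It describes the line plots as "illustrating the up-titration effect of treatment".

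No comparator, no run of earlier pre-escalation visits and no caution about selection is visible for these outputs. SAP 4 says in general that there is no formal testing and that p-values and confidence intervals are exploratory.

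**The concern.** A subject is more likely to be escalated after a bad spell than after a good one. If the value from that spell is also the starting point of the plot, later values will tend to be better even if the dose change does nothing, because some of the bad spell was ordinary fluctuation. A plot of escalated subjects alone cannot separate this from a dose effect, and calling the result an effect invites the causal reading.

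At stake is the interpretation of one set of descriptive displays. The Amendment 1 rationale puts the ASAS20 difference between the two doses at 20 percentage points. An artefact that is a sizeable share of that could be mistaken for confirmation of it.

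**Working it through.** **1. The plan's own yardstick.** The Amendment 1 rationale ties 150 mg exposure to about 60% ASAS20 response and 75 mg exposure to about 40%. 0.60 − 0.40 = 0.20, and 0.20 / 0.60 = 0.33. The stated 20% absolute and 33% relative differences reproduce. The documents give no figure for the up-titration analysis itself.

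**2. Is the before-value tied to the decision?** Protocol 6 requires visit procedures to be completed before dosing, and SAP 19.1 includes the day of the first up-titrated dose. An assessment made at an escalation visit therefore becomes the before-value. In Protocol Tables 6-1 to 6-3 the visible ASAS items (patient global and spinal pain VAS) are collected only at non-optional visits, 12 or 16 weeks apart. A subject escalated at an optional visit has a before-value 4, 8 or 12 weeks old. It is still affected if that result informed the judgement.

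**3. Size under judgement-based selection, zero dose effect.** All inputs here are assumed; the documents give neither the correlation nor the share escalated.

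- Latent response at each visit: Z = T + e, with var(T) = ρ and var(e) = 1 − ρ, so the correlation between visits is ρ.
- Responder if Z > c. For a 60% rate, c = −0.253.
- Investigator judgement: J = 0.8·Z₀ + 0.6·ε, where Z₀ is the decision-visit value and ε is independent standard normal noise. The lowest fraction f of J is escalated.
- Spurious gain = P(Z₁ > c | escalated) − P(Z₀ > c | escalated), where Z₁ is a later visit; 2,000,000 simulated subjects.

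| Share escalated | ρ = 0.6 | ρ = 0.8 | ρ = 0.9 |
|---|---|---|---|
| 25% | 14.0% → 34.7% (+20.7) | 14.0% → 25.2% (+11.2) | 14.0% → 19.8% (+5.8) |
| 50% | 31.7% → 44.5% (+12.8) | 31.8% → 38.8% (+7.0) | 31.8% → 35.4% (+3.6) |
| 75% | 47.6% → 52.3% (+4.7) | 47.8% → 50.0% (+2.2) | 47.7% → 48.7% (+1.0) |
| 100% | 0 | 0 | 0 |

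**4. Limiting case: only ASAS20 non-responders escalate.** The before-value is then 0% response, and the later rate is 1 − Φ₂(c, c; ρ) / (1 − p), where Φ₂ is the bivariate normal distribution function and p the response rate.

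- p = 0.60: ρ = 0.6 gives 1 − 0.2574/0.40 = 36%; ρ = 0.9 gives 1 − 0.3305/0.40 = 17%.
- p = 0.40 (c = +0.253): ρ = 0.6 gives 1 − 0.4574/0.60 = 24%; ρ = 0.9 gives 1 − 0.5305/0.60 = 12%.

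**5. Does an earlier before-value help?** In the model of step 3 with ρ = 0.8 and half the arm escalated, the decision-visit start gives 31.8% → 38.8% (+7.0). An earlier visit that did not enter the judgement gives 38.7% → 38.8% (+0.1).

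**The case against.** The case on the other side has real force on several points.

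- *The rule is not ASAS20 non-response.* It is an overall judgement that response is not fully achieved, after at least two years in the study, so an ASAS20 responder can be escalated. A reader might infer that escalated subjects were picked as non-responders at a trigger visit and that the percentages in step 4 apply. The documents do not support that; step 4 is a limiting case. This stands.
- *Escalation may be broad.* It opens when Amendment 1 is implemented, and that amendment calls 75 mg ineffective. If nearly the whole arm escalates, the artefact nearly vanishes. It also shrinks if the judgement rests on a long, stable history. This stands.
- *The 60% rate is an assumption.* The protocol ties 75 mg exposure to about 40%. In the limiting case this lowers the range from 17–36% to 12–24%. This stands.
- *The SAP specifies no before-after difference or test.* That is so, and it does not say outright that the plots display the before-value. But SAP 19.1 defines that value for the up-titration analysis, and SAP 14.1 uses the word effect.
- *Context exists.* Response is also shown by treatment sequence and for the originally randomized groups up to Week 260. These groups are not aligned to the time of escalation or selected in the same way. Part of SAP 5.1 and of the parameter list in SAP 14.1 is redacted, so the absence of a reference can be asserted only for the visible text.
- *Everything is exploratory.* That wording covers p-values and confidence intervals. It does not correct a starting point that depends on selection, or a causal label.

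A reader might also infer that the plots are meant to support the amendment. The amendment's argument rests on the Phase 3 arm comparisons and exposure data, and neither document assigns these plots that use.

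**Conclusion.** The mechanism is in the plan: selection on incomplete response, a before-value at or near the point of selection, escalated subjects only, and a plot described as showing an effect. Regression to the mean can therefore account for part of any rise. It does not follow that it accounts for all or most of it.

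The size is unknown. Under the step 3 assumptions it runs from nothing, if everyone escalates, to about the 20-point dose gap that the protocol cites, if a quarter escalate and visits correlate at 0.6. These results depend on the 60% rate, the 0.8 link between judgement and visit value, and the correlation range, none of which the documents give.

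This is a limited reporting point that is cheap to correct. The primary ASAS20 summary is unaffected, and nothing here bears on whether or when subjects should be escalated.

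**What to change.** In SAP 14.1 and 19.1:

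1. Call the plots *response after up-titration*, matching the description already used for the tables.
2. Show at least the two scheduled assessments that precede the last pre-escalation measurement, and keep that last measurement visible.
3. Take the before-value from those earlier assessments: the response rate at each for ASAS20/40, and their mean for any continuous measure.
4. State with the outputs that the display is uncontrolled and subject to regression to the mean.

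I would not add a reference row of 150 mg subjects who were ASAS20 non-responders at some visit. They would be selected by a stricter rule than the escalated subjects, could show more regression, and could over-correct.

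The cost is a little more programming on data already collected. The limit is that the earlier visits may also have informed the judgement, so the bias is reduced rather than surely removed.
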